2. OBJECTIVES

Overview and Purpose:

This project seeks to understand how someone already in a high-risk state will interpret genetic information informing risk of 'conversion' to a full disorder. How people interpret this possibility carries important consequences for how they choose to respond, which may range from fatalistic acceptance of the disorder to proactive preventative behavior. With the aim to encourage an active pro-health response, we propose developing two tools for communicating genetic risk and evaluate them regarding their effectiveness in inducing a positive response to the risk of illness. The two tools will consist of: 1) a clinician manual, designed to be used by a PhD level clinician with some genetic counseling training to communicate risk to CHR youth; 2) a high-impact, computerized tutorial ('AutoTutor') that has been used to convey genetic risk for breast cancer (i.e. BRCA gene). To create these 2 tools, experts in psychiatric genetics and stigma will work to develop the 2 tools to convey genetic risk information to youth and young adults identified as in a 'clinical high-risk state' (CHR) for psychosis. We assess primary outcomes of increased intent to engage in treatment and healthy behaviors, and a secondary outcome of reduction in stigma. While specific genes for risk of psychosis are not yet used in diagnosis or treatment, a genetic malleability (GM) framing conforms to the known genetic risk for psychosis, and has a strong likelihood of being used in the not too distant future. Because of the relatively large innovation involved, we seek to establish initial acceptability, safety, and efficacy of each tool. We then use a nonrandomized, within-subject, pre- vs. post design to examine whether providing the genetic malleability framing via each tool ($n=27$ CHR youth per tool, $N=54$ total) leads to improved outcomes. For each tool, participants will be conveyed hypothetical information proposing being identified as having a substantially elevated, genetically-malleable risk for developing psychosis.

Specific Aims and Hypotheses:

Aim 1: To develop 2 translational tools to convey a genetic malleability framing for psychosis-risk, we develop a clinician manual and a computerized AutoTutor to undergo acceptability, safety, and initial efficacy testing.

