Rationale: We evaluate tools that provide a genetic malleable (GM)framing, which has been linked with: a) greater agency, hope and optimism about recovery (Dar-Nimrod et al., 2014; Farrell, Lee, & Deacon, 2015); b) greater perceived odds of recovery, mood regulation(Lebowitz & Ahn, 2018) and less hopelessness (Lebowitz, Ahn, & Nolen-Hoeksema, 2013) in 3 experimental studies for depression, which persisted at 6 month follow-up (Lebowitz & Ahn, 2015). While people with psychosis show benefit from psychiatric genetic counseling (Inglis et al., 2015), access to such counselors is rare. Creating tools to beneficially convey GM framing for CHR adds greatly to public health.

Aim 2: To test whether CHR youth, after being exposed to the genetic malleability framing via each tool, will show greater endorsement of increased intent to engage in treatment and healthy behaviors and less stigma when compared with pre-exposure to the tool.

We predict that CHR youth, after receiving the GM framing via each tool, will show greater *intent to engage in treatment and healthy behaviors* and less *stigma* vs. pre-exposure.

-- As an exploratory analysis, we hypothesize that improvements in these outcomes will be associated with reductions in the mechanism of 'genetic essentialism'.

Re: the *exploratory analysis*, GM may benefit outcomes by reducing the mechanism of genetic essentialism (Farrell, Lee, & Deacon, 2015; Lebowitz, Ahn, & Nolen-Hoeksema,

2013). Studies have not tested mediating mechanisms when examining effects of genetic framings (Anido, Carlson, & Sherman, 2007; Dunn et al., 2008; Heshka et al., 2008). We will use identified mechanisms to convey beneficial results (i.e. that genes do not imply a fixed future) via the tools.

3. BACKGROUND, SIGNIFICANCE, AND RATIONALE:

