4. Identified as at clinical high risk for psychosis as defined as a)attenuated positive symptoms b)brief intermittent positive symptoms c) schizotypal disorder or family history of psychotic disorder with recent decline in functioning (30 GAF points)	Structured Interview for Psychosis-Risk Syndromes (SIPS)/Scale of Psychosis-Risk Symptoms (SOPS)

The exclusion criteria for COPE below are as follows:

EXCLUSION CRITERIA	METHOD OF ASCERTAINMENT
1. Psychosis diagnosis	Clinical interview and Structured Interview for Psychosis-Risk Syndromes (SIPS)/Scale of Psychosis-Risk Symptoms (SOPS)
2. History of neurological, neuroendocrine or other medical conditions known to affect the brain	Clinical interview and collateral information from patient's treaters (with their authorization for release)
3. IQ < 70	WTAR < 6
4. Moderate or severe risk of harm to self or others	Clinical interview, and Columbia Suicide Severity Rating Scale

Below are the Specific Inclusion Criteria for this protocol:

INCLUSION CRITERIA	METHOD OF ASCERTAINMENT
1. Male or females between the ages of 16-30	Phone screen and interview
2. Enrolled in COPE	Enrollment record

3. Identified as at clinical high risk for psychosis as defined as having at least one of the following: a)attenuated positive symptoms b)brief intermittent positive symptoms	Structured Interview for Psychosis-Risk Syndromes (SIPS)/Scale of Psychosis-Risk Symptoms (SOPS)
---	--

Below are the Exclusion criteria for this protocol:

EXCLUSION CRITERIA	METHOD OF ASCERTAINMENT
1.Meeting CHR via only the Genetic risk and deterioration (GRD) syndrome. If the participant meets the GRD syndrome only, we exclude the rare Genetic risk + deterioration (GRD) syndrome (comprising <1% of CHR cases) because GRD requires having a 1 st degree relative with any psychotic disorder, which may be linked with stronger reactions to genetic framings.	Clinical interview and Structured Interview for Psychosis-Risk Syndromes (SIPS)/Scale of Psychosis-Risk Symptoms (SOPS)
2. IQ < 80	The Test of Premorbid Functioning (TOPF)
3. Inability to adopt hypothetical situation	Hypothetical situation screener (see procedures section for description)

- Adults unable to consent (individuals with impaired decision making capacity)
 - Will not be included in this study
- Individuals who are not yet adults (infants, children, teenagers)
 - Will be included in this study (16-30 years old) (see inclusion/exclusion criteria)
- Pregnant women

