5. PROCEDURES

Study Timeline

Timeline	Month 0-2	Months 3-5	Months 6-22	Months 23-34
Task	Obtain IRB Approval	Develop 2 Tools	Test Tools (n=27 CHR youth/tool)	Refine Tools, Data Analysis + Manuscripts

Pre-Educational Session Protocol (Pre-Assessment):

Following successful enrollment into the study, and one-week prior to exposure to the educational session (either PsyGist or Clinician Manual), a trained research assistant will conduct pre-assessments. Participants will be assessed on: (1) covariates including socio-demographic variables, personality traits, exposure to genetic framing, barriers to mental health care, symptoms, cognition, quantification of perception of 'substantial psychosis risk' (0-100%) (2) 'genetic essentialism' (mechanism); (3) intent to engage in treatment and healthy behaviors (primary outcome); (4) stigma (secondary outcome). Data will be collected using REDCap with the exception of the following which may use an external site to collect data: (1) the Implicit Association Test for assessing stigma, and (2) the computerized behavioral task for assessing intent to engage in healthy behaviors. REDCap is a secure data collection tool that meets HIPAA compliance standards. REDCap will allow either the participant or the research assistant to fill out the measures being collected using this online tool.

Below is the information regarding the IAT and the new computerized behavioral tasks. We have updated the information concerning the administration of the website. While we don't plan to administer the IAT right now due to the study moving online, we may decide to administer this in the near future once we can better accommodate technical aspects of administration in an online format, while maintaining ethical standards.

Implicit Association Test (IAT): After completion of the pencil-and-paper stigma scale, participants will complete the IAT. The IAT will be administered on a secured and encrypted laptop. Research assistants will first review the instructions for the IAT, making certain that participants understand the process by which they must complete the task. Before starting the IAT, participants will be able to practice through the IAT's practice module.

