To accommodate recording during our virtual session and ensure participant confidentiality, we will ensure that the video part of the meeting is not recorded (i.e. the recording will be audio only; this feature is available via HIPAA-compliant video teleconferencing) and the audio recording will be saved to a secured laptop.

The research assistant will not be present for the 60-minute session but will reconvene with the participant for post-educational session assessments.

Study staff will be trained to administer a distress protocol (See description in "Post-Educational Session Protocol") throughout all phases of the study to monitor if participants exhibit signs of agitation, shaking or crying during or after exposure to the tool/ interview. The distress protocol will identify signs of distress, and prompt referral to a clinician. A clinician, either [name] (the director of COPE), [name] (chief psychologist at COPE), or our clinician who is administering our clinician manual ([name]), will be available for participants who require referral to a clinician based on the distress protocol.

Post-Educational Session Protocol:

Post-educational assessment protocol will be equivalent to pre-educational session assessment protocol, with the addition afterwards of the new computerized behavioral task and an acceptability assessment, followed by debriefing. Additionally, the following measures will be administered only as part of the pre-education session protocol: demographics, barriers to mental healthcare, exposure to genetic framing, life orientation test, tolerance for uncertainty.

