6. STATISTICAL ANALYSIS PLAN

We will assess variables’ distributions. We use bivariate tests to compare pre- vs post-intervention outcomes via paired t-test and Mann-Whitney Signed Rank tests. Primary and secondary outcomes will be assessed. We will stratify the sample by key covariates (e.g., IQ) and test for significant pre- vs post-mean difference scores by stratification.

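### Minor: testing pre-post change within strata of loosely named covariates cannot show whether change varies with them; one exploratory slope per pre-named covariate would

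*Combined protocol and SAP*

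**What the plan says.** Section 6 (Statistical Analysis Plan) is a single paragraph. The main analysis is paired: "We use bivariate tests to compare pre- vs post-intervention outcomes via paired t-test and Mann-Whitney Signed Rank tests". The sentence at issue follows shortly after: "We will stratify the sample by key covariates (e.g., IQ) and test for significant pre- vs post-mean difference scores by stratification".

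Other sections bear on how to read it:

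- **Unit of analysis.** Section 2 frames the question per tool: "We then use a nonrandomized, within-subject, pre- vs. post design to examine whether providing the genetic malleability framing via each tool" improves outcomes, with 27 people per tool and 54 in all. Aim 2 uses the same per-tool wording ("after being exposed to the genetic malleability framing via each tool").
- **Covariates.** Section 5 (pre-assessment) lists "covariates including socio-demographic variables, personality traits, exposure to genetic framing, barriers to mental health care, symptoms, cognition" and then perceived psychosis risk on a 0-100% scale. That makes seven groups, and none is marked as key.
- **IQ.** Section 4 excludes people with IQ below 80, so IQ is held as a number.
- **Outcomes.** Section 5 says "Post-educational assessment protocol will be equivalent to pre-educational session assessment protocol", but adds the computerised behavioural task after the session. Not every measure therefore clearly has a pre value.
- **Status.** The exploratory label in Section 2 is attached to the genetic-essentialism analysis, not to the stratified tests.

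**The concern.** The usual reason to stratify by IQ is to learn whether people with higher or lower IQ change more. A separate pre-post test in each stratum asks something else: whether change differs from zero in that stratum. One significant and one non-significant result can easily arise when the true change is the same in both, and the SAP has no sentence warning against reading such a pair as a subgroup difference.

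If the sentence instead means that change is compared between strata, the question is right but the method wastes information, because a numeric score is cut into groups. If it is only a descriptive look, means with confidence intervals are enough and no significance test is needed. Each reading points to a better sentence.

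The stakes are limited to this subsidiary analysis: a misread pattern on the first reading, or a real relation missed more often than necessary on the second.

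**Working it through.** **Inputs from the documents:** 27 per tool, 2 × 27 = 54 in total; paired tests; IQ as the one example; two outcome constructs (intent, stigma). The documents give no alpha, effect size, SD or power, so there is no sample-size calculation to reproduce.

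**Assumptions, not in the documents:** two-sided 0.05; two strata; the effect sizes and correlations stated below.

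**1. Within-stratum reading.** Let *d* be mean change divided by the SD of change, equal in both strata. Let *p* and *q* be the paired t-test power in the two strata (noncentral t). The chance that exactly one stratum is significant is *p*(1 − *q*) + *q*(1 − *p*).

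| *d* | Power, n = 13 / 14 | Exactly one (13/14) | Power, n = 27 | Exactly one (27/27, pooled) |
|---|---|---|---|---|
| 0 | 0.05 / 0.05 | 10% | 0.05 | 10% |
| 0.3 | 0.169 / 0.180 | 29% | 0.324 | 44% |
| 0.56 | 0.459 / 0.492 | 50% | 0.80 | 32% |
| 0.8 | 0.754 / 0.790 | 35% | 0.979 | 4% |

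For example, at *d* = 0.56 with 13 and 14: 0.459 × 0.508 + 0.492 × 0.541 = 0.499. Pooled: 2 × 0.80 × 0.20 = 0.32. At *d* = 0.56 all 27 people in one tool have 80% power, while each half has 46% or 49%. A non-significant half therefore says little.

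**2. Between-strata reading.** Take 27 people, a pre-post correlation of 0.6, and a covariate independent of baseline. Let *r* be its partial correlation with change given baseline. With unit variances, the variance of change is 2(1 − 0.6) = 0.80, and its variance given baseline is 1 − 0.6² = 0.64. The plain correlation with change is *r* × √(0.64/0.80) = 0.894*r*, that is 0.27, 0.36 and 0.45 at *r* = 0.3, 0.4 and 0.5. Simulated power with no baseline term, as in the SAP (repeat runs agree to about one point):

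| *r* | Median split | Continuous slope |
|---|---|---|
| 0.3 | 19% | 28% |
| 0.4 | 30% | 47% |
| 0.5 | 46% | 67% |

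If the tools are pooled (54 people) and the correlation is taken directly with change, power at 0.3, 0.4 and 0.5 is 42, 66 and 87% for the split against 61, 86 and 98% for the slope.

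**3. Should baseline be in the model?** Suppose there is no true relation, with 27 people, a pre-post correlation of 0.6 and a covariate-baseline correlation of 0.3, 0.4 or 0.5.

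- If the covariate tracks the observed baseline, the unadjusted slope is significant in 10, 15 and 20% of trials and the adjusted slope in 5%.
- If it tracks only the stable part of baseline, the adjusted slope is significant in 12, 19 and 30% and the unadjusted slope in 5%.

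Neither model is safe in both cases. The unadjusted slope answers the question of who changes more, so it comes first and the adjusted one is a sensitivity analysis.

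**4. Multiplicity of the proposed analysis.** Three covariates × 2 tools × 2 outcomes = 12 slopes. If independent, the chance of at least one false positive is 1 − 0.95¹² = 46%. With seven covariates there are 28 slopes and 1 − 0.95²⁸ = 76%.

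**The case against.** The strongest reply is that no error has been shown. The SAP does not say it will compare strata or claim subgroup effects, the sentence has more than one reading, and this is an early development study meant to inform a later randomised trial. That stands, and it is why the point is minor and optional.

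A reader might infer that the plan would produce false subgroup claims in 29 to 50% of trials. The documents do not support this: those figures are rates of discordant p-values, which mislead only if someone reads them as a difference.

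A reader might also take strata of 13 and 14 as given. Aim 2 favours a per-tool analysis, but Section 6 speaks only of the sample, which could be all 54, so both cases are shown. Pooling does not remove the problem: discordance is higher at *d* = 0.3 and lower at 0.56.

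Finally, a reader might conclude that baseline must be in the model. That is a trade-off rather than a correction, as the third step of the working shows.

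It is also fair to say that the remedy has its own multiplicity and that its power at 27 is low. Both are true and are counted as costs.

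**Conclusion.** The point holds as a minor, optional improvement to a subsidiary analysis. Nothing elsewhere in the documents supplies a comparison of strata, cut-points, a choice of key covariates or an exploratory label for this analysis. On the natural within-stratum reading, the p-values cannot answer whether change varies with the covariate. On the between-strata reading, a median split gives up roughly 9 to 21 percentage points of power at 27 people (28 − 19 = 9; 67 − 46 = 21).

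The figures rest on an assumed two-sided 0.05, two strata, identical true change for the discordance rates, and a pre-post correlation of 0.6 with a covariate independent of baseline for the power figures. The direction of both results does not depend on these values; the size does.

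It would go too far to say that the trial's conclusions are at risk: the main pre-post comparison is untouched. Nor are the covariates wholly undefined, since Section 5 lists the groups. What is missing is which of them are key.

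**What to change.** Replace the stratification sentence in Section 6 with text such as:

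> For each tool and each outcome measured at both visits, change (post minus pre) is regressed on each of a short, pre-named list of covariates, one at a time. Numeric covariates such as IQ stay continuous; categorical ones enter as categories. The slope or between-category difference is reported with a 95% CI. The baseline-adjusted estimate is shown as a labelled sensitivity analysis. Stratum means may be shown descriptively with CIs, and no subgroup claim is drawn from within-stratum p-values. If tools are pooled, tool is a term. These analyses are exploratory; with no control group, a slope describes who changes more, not effect modification.

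The cost is SAP wording only, since the covariates and pre-session values are already to be collected. The downsides should be accepted openly:

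- Linearity is assumed.
- Power at 27 is low (67% even at *r* = 0.5).
- The unadjusted slope can reflect regression to the mean if the covariate tracks the observed baseline.
- The false-positive rate grows quickly with the number of covariates, so the list must be short and the results treated as exploratory.

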7. DATA MANAGEMENT

Confidentiality of all participants will be preserved by coding all datasheets and other data sources and maintaining them in locked files/drawers in the study clinicians office/PI’s office or will be kept on a secure computer by the study clinician/PI. ID numbers will be determined by order of participant entry into the study and will not be related in any way to participant

identifying data (i.e., the first participant who is recruited into the study will be subject #1, etc.). Data will be entered into a computerized database. The database is on a computer, which requires a password to access the data. Public dissemination of the results of this research will be reported on subjects collectively and will contain no identifying information about individual participants.

A deidentified dataset will be transmitted from [name] to [name] (PI) at NYU only via encrypted, password protected files via secure email or an encrypted flashkey.

To accommodate the virtual administration of this protocol and ensure confidentiality, we will use a telephone or HIPAA-compliant video teleconferencing. We believe this will ensure that the virtual meeting is secure.

Protocol Violations

Any deviations from the IRB protocol will be first reviewed by BRANY's IRB and will subsequently be submitted in the annual progress report to NHGRI's Program Officer and to the DSMB.

Unanticipated Problems

Unexpected incidents, experiences or outcomes that are potentially related to participation and suggest that the research places the participants at a greater risk of harm than was previously known or recognized, will be reported to the NHGRI Program Officer, the DSMB, and the IRB within 10 business days of the study team becoming aware of the event.

Discontinuation criteria

Regarding discontinuation criteria and who will determine if a participant is too ill to continue to participate, a participant will discontinue the study under the following conditions: (1) if the participant decides not to continue the study for personal reasons; and (2) if the patient presents with acute or imminent harm to themselves or others, or suffers other incapacitating conditions (i.e., exacerbation of prodromal psychosis symptoms to the point of requiring in patient hospitalization) he or she may be removed from the study; and (3) if the participant develops full symptoms due to psychosis. In all cases, the participant's treating clinician will consult with the PI and be informed about the discontinuation of study participation.

Data Safety and Monitoring Board:

Given that the proposed study is an NIH-defined Phase I clinical trial, and that we are recruiting children, a Data and Safety Monitoring Board will be appointed. Members of the DSMB will include three established and well-recognized experts in stigma and psychosis/CHR who are doctoral-level clinicians and researchers who have had at least 5 years of clinical experience working with psychosis/CHR. The following members will comprise the DSMB, all of whom have no affiliation or role in the project: [name], [name], and [name]. The DSMB will convene every six months and in the event of a serious adverse event.

Review/monitoring activities will include reviewing the protocol, risk-benefit considerations, informed consent documents and plans for data safety and monitoring; evaluating the progress of the study, including periodic assessments of data quality and timeliness, participant recruitment, accrual and retention; and other factors that can affect study outcomes; considering factors external to the study such as scientific or therapeutic developments that may have an impact on the safety of the participants; protecting the safety of the study participants and reporting on the safety and scientific progress of the trial. In addition to having the power to recommend to the PI that the study be stopped or modified, the DSMB can determine whether

any adverse event or serious adverse event affects the risk-benefit ratio of the study, and whether modifications to the protocol or consent forms are required.

REFERENCES:

